#### 14.4 HCV-PRO to measure well-being and functioning (Aim 1c, 3b, 4d)

The HCV-PRO is a newly developed survey designed to assess the well-being and functional status of patients with HCV. It was developed in accordance with the PRO guidelines issued by the US FDA and demonstrated good reliability and convergent validity was moderate-high ( $r > 0.50$ ). HCV-PRO items measure physical, emotional and social functioning, productivity, intimacy, and perception of quality of life. Participants select responses from a 5-point Likert scale: 1=“all of the time” to 5=“none of the time”. A higher total score indicates higher functioning.

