#### **15.3 Supportive longitudinal analysis and interpretation of changes from baseline**

HCV-related symptom scores will be measured longitudinally. As an aid to interpretation of the primary results, and for purposes of generating new hypotheses, auxiliary longitudinal analyses of these repeated measures may also be explored.

Any increments from Baseline (T1) during treatment (T2/T3) will represent worsening of HCV-related symptoms or commencement of new onset treatment side effects. Similarly, decrements from Treatment (T2/T3) to 12-weeks post-treatment (T4) will represent amelioration or disappearance of symptoms. For any

symptoms remaining at T4, decrements from T4 to T5 will represent further healing. Thus for each individual the longitudinal trajectories of the scores represents that individual's history of waxing and/or waning of HCV-related symptoms. Secondarily, complementary analyses of each of the 32 symptoms will be used to investigate whether side effects that begin during treatment tend to resolve and to investigate the incidence of new symptoms or side effects that appear after treatment ends.

Treatment-related side-effects scores will also be measured longitudinally. Ideally, any increment from T1 to T2/T3 will be completely reversed by a decrement from T2/T3 to T4 or T5. Thus for each individual, the longitudinal trajectories of the scores represents that individual's history of waxing and/or waning treatment-related side-effects and HCV-related symptoms. These trajectories will be summarized descriptively via estimates of occasion-specific mean levels (with confidence intervals) and in terms of patterns of the trajectories represented, for example, by the proportion of patients for whom all treatment-related side-effects disappeared by T4/T5.

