## 2. Tabular Summary of Performance Curve Figures

PRO\_measure = MSAS with Conjectures = { SD = 0.6 [0.45, 0.75] and serial correlation is R = 0.50 }

a difference of 0.10 points on the MSAS scale will be considered clinically important

Figure	MS	Groups	N	procedure	X_80	X_90
1-1	1, 3, 4	1	1500	Confidence interval [1]	0.03 [0.02,0.04]	0.03 [0.02,0.04]
1-2	1, 3, 4	1	960	Confidence interval [1]	0.04 [0.03,0.05]	0.04 [0.03,0.05]
1-3	1, 3, 4	1	160	Confidence interval [1]	0.10 [0.07,0.12]	0.10 [0.08,0.13]
1-4	1, 3, 4	1	120	Confidence interval [1]	0.11 [0.09,0.14]	0.12 [0.09,0.15]
1-5	1, 3, 4	1	100	Confidence interval [1]	0.13 [0.09,0.16]	0.13 [0.10,0.16]
1-6	1, 3, 4	1	80	Confidence interval [1]	0.14 [0.11,0.18]	0.15 [0.11,0.18]
1-7	1, 3, 4	1	1500	test Ho: 'mean change is zero' [2]	0.04 [0.03,0.05]	0.05 [0.04,0.06]
1-8	1, 3, 4	1	960	test Ho: 'mean change is zero' [2]	0.05 [0.04,0.07]	0.06 [0.05,0.08]
1-9	1, 3, 4	1	160	test Ho: 'mean change is zero' [2]	0.13 [0.10,0.17]	0.15 [0.12,0.19]
1-10	1, 3, 4	1	120	test Ho: 'mean change is zero' [2]	0.15 [0.12,0.19]	0.18 [0.13,0.22]
1-11	1, 3, 4	1	100	test Ho: 'mean change is zero' [2]	0.17 [0.13,0.21]	0.20 [0.15,0.25]
1-12	1, 3, 4	1	80	test Ho: 'mean change is zero' [2]	0.19 [0.14,0.24]	0.22 [0.17,0.28]
1-13	1, 3A, 4	2	800 + 800	test Ho: 'mean diff. is zero' [3]	0.08 [0.06,0.11]	0.10 [0.07,0.12]
1-14	1, 3A, 4	2	1500 + 100	test Ho: 'mean diff. is zero' [3]	0.18 [0.13,0.22]	0.20 [0.15,0.25]
1-15	1, 3A, 4	2	400 + 400	test Ho: 'mean diff. is zero' [3]	0.12 [0.09,0.15]	0.14 [0.10,0.17]
1-16	1, 3A, 4	2	160 + 120	test Ho: 'mean diff. is zero' [3]	0.20 [0.15,0.25]	0.24 [0.18,0.29]
1-17	1, 3A, 4	2	160 + 80	test Ho: 'mean diff. is zero' [3]	0.23 [0.17,0.29]	0.27 [0.20,0.33]
1-18	1, 3A, 4	2	80 + 80	test Ho: 'mean diff. is zero' [3]	0.27 [0.20,0.33]	0.31 [0.23,0.39]
1-19	1, 3A, 4	2	960 + 80	test Ho: 'mean diff. is zero' [3]	0.20 [0.15,0.25]	0.23 [0.17,0.29]
1-20	1, 3A, 4	2	960 + 160	test Ho: 'mean diff. is zero' [3]	0.14 [0.11,0.18]	0.17 [0.13,0.21]

[1]  $\Pr[\text{Confidence Interval's half-width will be } < X_{80}] = 0.80$

[2]  $\Pr[p < \alpha | \text{population mean change} = X_{80}] = 0.80$

[3]  $\Pr[p < \alpha | \text{population mean difference} = X_{80}] = 0.80$

[4]  $\Pr[p < \alpha | \text{population rate change} = X_{80}] = 0.80$

[5]  $\Pr[p < \alpha | \text{population rate difference} = X_{80}] = 0.80$

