**PRO\_measure = PROMIS      with Conjectures = { SD = 10 [6, 12] and serial correlation is R = 0.50 }**

**a difference of 3 points on a PROMIS scale will be considered clinically important**

Figure	MS	Groups	N	procedure	X_80	X_90
2-1	1, 3, 4	1	1500	Confidence interval [1]	0.52 [0.31,0.62]	0.52 [0.31,0.63]
2-2	1, 3, 4	1	960	Confidence interval [1]	0.65 [0.40,0.78]	0.66 [0.41,0.79]
2-3	1, 3, 4	1	160	Confidence interval [1]	1.63 [0.98,1.96]	1.67 [1.01,2.01]
2-4	1, 3, 4	1	120	Confidence interval [1]	1.90 [1.14,2.29]	1.96 [1.18,2.35]
2-5	1, 3, 4	1	100	Confidence interval [1]	2.10 [1.26,2.52]	2.16 [1.30,2.60]
2-6	1, 3, 4	1	80	Confidence interval [1]	2.37 [1.42,2.84]	2.45 [1.47,2.94]
2-7	1, 3, 4	1	1500	test Ho: 'mean change is zero' [2]	0.72 [0.44,0.87]	0.84 [0.50,1.01]
2-8	1, 3, 4	1	960	test Ho: 'mean change is zero' [2]	0.91 [0.54,1.09]	1.05 [0.63,1.26]
2-9	1, 3, 4	1	160	test Ho: 'mean change is zero' [2]	2.23 [1.34,2.67]	2.58 [1.55,3.09]
2-10	1, 3, 4	1	120	test Ho: 'mean change is zero' [2]	2.58 [1.55,3.09]	2.98 [1.79,3.58]
2-11	1, 3, 4	1	100	test Ho: 'mean change is zero' [2]	2.83 [1.70,3.39]	3.27 [1.96,3.93]
2-12	1, 3, 4	1	80	test Ho: 'mean change is zero' [2]	3.17 [1.90,3.81]	3.67 [2.20,4.40]
2-13	1, 3A, 4	2	800 + 800	test Ho: 'mean diff. is zero' [3]	1.40 [0.84,1.68]	1.62 [0.97,1.95]
2-14	1, 3A, 4	2	1500 + 100	test Ho: 'mean diff. is zero' [3]	2.92 [1.75,3.50]	3.38 [2.03,4.05]
2-15	1, 3A, 4	2	400 + 400	test Ho: 'mean diff. is zero' [3]	1.98 [1.19,2.38]	2.29 [1.38,2.75]
2-16	1, 3A, 4	2	160 + 120	test Ho: 'mean diff. is zero' [3]	3.40 [2.04,4.08]	3.93 [2.36,4.72]
2-17	1, 3A, 4	2	160 + 80	test Ho: 'mean diff. is zero' [3]	3.86 [2.32,4.63]	4.47 [2.68,5.36]
2-18	1, 3A, 4	2	80 + 80	test Ho: 'mean diff. is zero' [3]	4.46 [2.67,5.35]	5.16 [3.09,6.19]
2-19	1, 3A, 4	2	960 + 80	test Ho: 'mean diff. is zero' [3]	3.29 [1.98,3.95]	3.81 [2.29,4.57]
2-20	1, 3A, 4	2	960 + 160	test Ho: 'mean diff. is zero' [3]	2.40 [1.44,2.88]	2.78 [1.67,3.34]

[1]  $\Pr[\text{Confidence Interval's half-width will be } < X_{80}] = 0.80$

[2]  $\Pr[p < \alpha | \text{population mean change} = X_{80}] = 0.80$

[3]  $\Pr[p < \alpha | \text{population mean difference} = X_{80}] = 0.80$

[4]  $\Pr[p < \alpha | \text{population rate change} = X_{80}] = 0.80$

[5]  $\Pr[p < \alpha | \text{population rate difference} = X_{80}] = 0.80$

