**PRO\_measure = HCV-PRO with Conjectures = { SD = 25.92 [23.641, 28.835] and serial correlation is R = 0.50 }**

**a difference of 10 points on the HCV-PRO scale will be considered clinically important**

Figure	MS	Groups	N	procedure	X_80	X_90
3-1	1, 3, 4	1	1500	Confidence interval [1]	1.34 [1.24,1.50]	1.35 [1.26,1.51]
3-2	1, 3, 4	1	960	Confidence interval [1]	1.67 [1.54,1.88]	1.71 [1.57,1.90]
3-3	1, 3, 4	1	160	Confidence interval [1]	4.23 [3.86,4.71]	4.34 [3.96,4.83]
3-4	1, 3, 4	1	120	Confidence interval [1]	4.94 [4.50,5.49]	5.07 [4.63,5.64]
3-5	1, 3, 4	1	100	Confidence interval [1]	5.44 [4.96,6.05]	5.61 [5.11,6.24]
3-6	1, 3, 4	1	80	Confidence interval [1]	6.14 [5.60,6.83]	6.35 [5.79,7.06]
3-7	1, 3, 4	1	1500	test Ho: 'mean change is zero' [2]	1.88 [1.71,2.09]	2.17 [1.98,2.42]
3-8	1, 3, 4	1	960	test Ho: 'mean change is zero' [2]	2.35 [2.14,2.61]	2.71 [2.48,3.02]
3-9	1, 3, 4	1	160	test Ho: 'mean change is zero' [2]	5.78 [5.27,6.42]	6.68 [6.10,7.43]
3-10	1, 3, 4	1	120	test Ho: 'mean change is zero' [2]	6.68 [6.10,7.43]	7.73 [7.05,8.60]
3-11	1, 3, 4	1	100	test Ho: 'mean change is zero' [2]	7.33 [6.69,8.16]	8.48 [7.74,9.44]
3-12	1, 3, 4	1	80	test Ho: 'mean change is zero' [2]	8.22 [7.50,9.14]	9.51 [8.67,10.58]
3-13	1, 3A, 4	2	800 + 800	test Ho: 'mean diff. is zero' [3]	3.63 [3.31,4.04]	4.20 [3.83,4.68]
3-14	1, 3A, 4	2	1500 + 100	test Ho: 'mean diff. is zero' [3]	7.56 [6.90,8.41]	8.75 [7.98,9.74]
3-15	1, 3A, 4	2	400 + 400	test Ho: 'mean diff. is zero' [3]	5.14 [4.69,5.72]	5.95 [5.43,6.62]
3-16	1, 3A, 4	2	160 + 120	test Ho: 'mean diff. is zero' [3]	8.80 [8.03,9.79]	10.19 [9.29,11.33]
3-17	1, 3A, 4	2	160 + 80	test Ho: 'mean diff. is zero' [3]	10.00 [9.12,11.13]	11.58 [10.56,12.88]
3-18	1, 3A, 4	2	80 + 80	test Ho: 'mean diff. is zero' [3]	11.55 [10.54,12.85]	13.37 [12.19,14.87]
3-19	1, 3A, 4	2	960 + 80	test Ho: 'mean diff. is zero' [3]	8.54 [7.79,9.50]	9.88 [9.01,10.99]
3-20	1, 3A, 4	2	960 + 160	test Ho: 'mean diff. is zero' [3]	6.23 [5.68,6.93]	7.21 [6.57,8.02]

[1]  $\Pr[\text{Confidence Interval's half-width will be } < X_{80}] = 0.80$

[2]  $\Pr[p < \alpha | \text{population mean change} = X_{80}] = 0.80$

[3]  $\Pr[p < \alpha | \text{population mean difference} = X_{80}] = 0.80$

[4]  $\Pr[p < \alpha | \text{population rate change} = X_{80}] = 0.80$

[5]  $\Pr[p < \alpha | \text{population rate difference} = X_{80}] = 0.80$

PRO\_measure = ADHERENCE

with Conjectures = { rate P1 = 0.80 [0.60, 0.90] }

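### Section 15.3 reads falls in symptoms still present at T4 as healing, but selecting on T4 status produces falls by regression to the mean, of a size set by the unstated share selected

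*Combined protocol and SAP*

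**What the plan says.** Section 15.3 covers the supportive longitudinal analysis of symptom and side-effect scores. It gives a meaning to movement in each interval: rises from T1 to T2/T3 are worsening or new side effects, falls to T4 are amelioration, and for any "symptoms remaining at T4, decrements from T4 to T5 will represent further healing". It then says that each person's trajectory shows that person's symptoms coming and going. It does not define when a symptom counts as remaining, and it does not mention measurement error, regression to the mean or a comparison group.

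The same section plans two relevant summaries. One is the mean level at each visit with confidence intervals, together with patterns such as the proportion whose side effects have all gone by T4/T5. The other is a complementary look at the 32 MSAS symptoms, covering whether side effects resolve and whether new symptoms appear after treatment. The section labels this work auxiliary, as an aid to interpretation and a source of new hypotheses.

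The Appendix for Sample Size Analyses (part 2) gives the plan's working figures. For MSAS they are "SD = 0.6 [0.45, 0.75] and serial correlation is R = 0.50", and "a difference of 0.10 points on the MSAS scale will be considered clinically important". For PROMIS they are "SD = 10 [6, 12] and serial correlation is R = 0.50", and "a difference of 3 points on a PROMIS scale will be considered clinically important".

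**The concern.** The sentence looks only at symptoms that are present at T4 and attaches a cause to their fall. When two visits correlate below 1, people chosen for a high score or a reported symptom at the first visit score lower on average at the second, even if nothing has changed. People without the symptom at the first visit drift up by an offsetting amount. The sentence gives meaning to the first movement only. New symptoms are looked at elsewhere in 15.3, but nothing says that the two are to be set against each other.

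At stake is what the supportive analysis may conclude. Section 15.8 uses auxiliary longitudinal analyses to help interpret the one-year results of Manuscript #4. A reading fixed in advance that can return healing in a stable population could lend false support to a statement about late benefit.

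**Working it through.** **Step 1. How the plan uses its correlation.** With SD s and correlation R, the SD of a change is s × √(2(1 − R)), which equals s at R = 0.50. For PROMIS this is 10. For 80 + 80 participants, two-sided α = 0.05 and 80% power, the normal approximation gives (1.960 + 0.842) × 10 × √(2/80) = 4.43, and the noncentral t gives 4.457. The appendix states 4.46. MSAS with 80 + 80 gives 0.267 (stated 0.27). A baseline-adjusted SD of 10 × √(1 − 0.50²) = 8.66 would give 3.86, which does not match. So R = 0.50 enters the plan as a visit-to-visit correlation of raw scores. It is a planning conjecture; the documents give no separate value for T4 with T5, which are about nine months apart.

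**Step 2. Expected fall with no true change.** Take scores at T4 and T5 as bivariate normal with equal means, and select the share p above a cut-off c at T4:

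fall = (1 − R) × s × φ(c)/p

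The share p is an assumption, because the documents give none. At R = 0.50, with the plan's SD range in brackets:

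| Share selected | φ(c)/p | MSAS fall (important difference 0.10) | PROMIS fall (important difference 3) |
|---|---|---|---|
| 50% | 0.798 | 0.6 × 0.5 × 0.798 = 0.24 [0.18, 0.30] | 10 × 0.5 × 0.798 = 3.99 [2.39, 4.79] |
| 80% | 0.350 | 0.105 [0.079, 0.131] | 1.75 [1.05, 2.10] |
| 90% | 0.195 | 0.058 [0.044, 0.073] | 0.98 [0.585, 1.17] |

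Simulation agrees: 0.398 SD at 50% and 0.174 SD at 80%, against 0.399 and 0.175 from the formula. With no selection the fall is zero.

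**Step 3. Where the fall passes the important difference.** At R = 0.50 and central SDs it does so only if less than about 81% (MSAS) or 63% (PROMIS) is selected. Over the SD ranges those limits run from 74% to 85% and from 38% to 70%. With the upper half selected, the correlation at which the fall equals the important difference is 1 − 0.10/(0.6 × 0.798) = 0.79 for MSAS and 1 − 3/(10 × 0.798) = 0.62 for PROMIS. At R = 0.70 the PROMIS fall is 10 × 0.3 × 0.798 = 2.4.

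**Step 4. Selection as any MSAS score above zero.** MSAS has a floor, so normality is rough here. If the T4 mean is μ and a share p scores above zero, the selected mean is μ/p. With a linear regression of T5 on T4, the fall is (1 − R) × μ × (1 − p)/p. For assumed μ of 0.3, 0.6 or 0.9, it exceeds 0.10 only if less than 60%, 75% or 82% still report a symptom. At 90% it is 0.02 to 0.05.

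**Step 5. One person.** For one unselected person with no true change, the chance of any fall is 50%. The chance of a fall beyond the important difference is P(Z > 0.10/0.6) = 43% on MSAS and P(Z > 3/10) = 38% on PROMIS. The plan states these differences for means, so using them for one person is only a yardstick.

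**Step 6. One symptom.** As an illustration, assume 30% prevalence at both visits and a correlation of 0.50 for presence. Of those with the symptom at T4, (1 − 0.50) × (1 − 0.30) = 35% lack it at T5. Of those without it, 0.50 × 0.30 = 15% gain it. The flows cancel: 0.30 × 0.35 = 0.70 × 0.15 = 0.105. At a correlation of 0.70, 21% resolve. Resolution alone would be read as healing although prevalence is unchanged.

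HCV-PRO is left out, because on that scale "A higher total score indicates higher functioning", so a fall is a worsening.

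**The case against.** The strongest reply is that 15.3 specifies no subgroup selected at T4, no cut-off and no T4-to-T5 estimate within one. Reference to remaining symptoms may be a plain qualifier, since only a symptom that is present can decrease. The first summary the section names, the mean at each visit, is not conditioned on T4 status, so this artefact is zero there. Onset of new symptoms is already to be examined. The work is optional and exploratory.

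Most of this stands, and it limits the point. It does not remove it: the section still says without qualification what a fall represents, carries that to individual trajectories, and does not tie resolution to onset.

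A reader might infer two stronger things. The first is that R = 0.50 alone makes the artefact larger than the important difference. It does not, because the result also needs the share selected. With 90% selected the fall is below the important difference on both scales, and PROMIS misses it with the upper half selected at SD 6 (2.39) or at R = 0.70. The second is that the main long-term result is compromised. The documents do not support that: Aim 4 and the models in 15.8 concern change from T1 to T5 adjusted for the baseline score, and no numbered aim is a T4-to-T5 contrast.

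**Conclusion.** The point holds as a minor one. Applied to individuals or to symptoms selected as present at T4, the interpretation in 15.3 can report healing in a stable population. Between selecting 50% and 90% at T4, the expected spurious fall runs from 0.24 to 0.058 on MSAS and from 3.99 to 0.98 on PROMIS, so it lies above or below the important difference depending on a share that the plan leaves open. These figures assume R = 0.50 between T4 and T5, central SDs, equal means at both visits and approximate normality. A higher correlation shrinks them in proportion to 1 − R. Only the supportive, hypothesis-generating analysis is affected. The primary T1-to-T5 models and the visit means are not affected by this selection.

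**What to change.** Replace the sentence in 15.3 so that decrements from T4 to T5 are described as change, not healing, and define when a symptom counts as remaining. Base any statement about late improvement on T4-to-T5 change in all participants with both surveys, without selecting on T4 status. For single symptoms, report resolution among those with the symptom at T4 together with onset among those without it, and interpret the net change in prevalence. Individual trajectories can still be described.

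A comparison with participants without SVR is optional and descriptive only. About 100 are expected, and for 1500 + 100 the appendix gives an MSAS difference of 0.18 at 80% power, above the important difference of 0.10.

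The cost is SAP wording, slightly more tabulation and a more cautious interpretation. No new data are needed.

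### Section 15.3's individual-level reading of rises and recovery has no no-effect reference and can rank a harmless regimen below a harmful one

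*Combined protocol and SAP*

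**What the plan says.** Section 15.3 gives a reading rule for scores: "Any increments from Baseline (T1) during treatment (T2/T3) will represent worsening of HCV-related symptoms or commencement of new onset treatment side effects". The section applies this to each individual's trajectory and attaches no minimum size of change.

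On recovery it says: "Ideally, any increment from T1 to T2/T3 will be completely reversed by a decrement from T2/T3 to T4 or T5". Trajectories are to be described by means at each visit with confidence intervals, and also by patterns, one example being "the proportion of patients for whom all treatment-related side-effects disappeared by T4/T5". The section does not define treatment-related or disappeared, does not give a denominator, and does not say whether T4/T5 means T4, T5, either or both.

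Two other statements in 15.3 set the context. The status of the work is that "auxiliary longitudinal analyses of these repeated measures may also be explored". In addition, "complementary analyses of each of the 32 symptoms will be used to investigate whether side effects that begin during treatment tend to resolve".

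Elsewhere, section 15.12 and the Appendix give important differences of 0.10 (MSAS), 3 (PROMIS) and 10 (HCV-PRO), used for mean changes and group differences. Section 15.5 takes the larger of T2 and T3 as the on-treatment score. Sections 15.7 and 15.8 model mean change from T1 to T4 and from T1 to T5.

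**The concern.** Symptom scores move between visits without any treatment effect; the Appendix itself assumes a serial correlation of only 0.50. If every rise is read as worsening or a side effect, ordinary fluctuation is counted as harm. Patients picked out by a rise also tend to have had a low T1 score by chance, so a return to their usual level need not bring them back to T1 and can look like incomplete recovery.

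Whether side effects resolve is central to the study's stated purpose for patients (Brief Summary and section 2). A percentage with all side effects gone is easy to quote, and a reader would naturally take 100% as the value for a harmless regimen. If the true no-effect value is far below that, a regimen could be described as leaving unresolved harm that it never caused.

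**Working it through.** **1. Inputs.** The Appendix table for PROMIS gives "SD = 10 [6, 12] and serial correlation is R = 0.50". Hence SD of change = 10 × √(2 × (1 − 0.50)) = 10.

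**2. Reproducing the plan's own figures.** Section 15.3 states no figure, so this checks the inputs against the PROMIS table.
- Half-width at N = 80 with 80% assurance: t(0.975, 79) × 10/√80 × √(χ²(0.80, 79)/79) = 1.990 × 1.118 × 1.063 = 2.37 (stated 2.37). N = 160 and 960 give 1.63 and 0.65, as stated.
- Power for a difference of 4.46 with 80 + 80: standard error 10 × √(2/80) = 1.581; 4.46/1.581 − 1.96 = 0.86, about 80% (stated 80%).

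**3. One score, no treatment effect.** Assume equal means, equal correlation across visits and no ties. All rank orders are then equally likely, so the results do not depend on the SD or on the size of the correlation.
- P(T2 > T1) = 1/2.
- P(larger of T2, T3 > T1) = 1 − 1/3 = 2/3.
- Risen, and still above T1 at T4: 1/2 − 2/24 = 5/12, or 42% of all patients. Reversed among risers: 1 − (5/12)/(2/3) = 37.5%.
- Risen, and above T1 at both T4 and T5: 1/3 − 4/120 = 3/10, or 30% of all patients. Reversed at T4 or T5 among risers: 1 − (3/10)/(2/3) = 55%.

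Simulation of 1,000,000 patients with correlation 0.50 agrees.

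**4. Sensitivity.** If correlation decays with the gap between visits (0.7 per visit), 54% of risers fail T4 or T5, so 46% pass. If scores move in 5-point steps, 38% fail and 62% pass.

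**5. Can the figure tell the cases apart?** Simulation, PROMIS SD 10 and correlation 0.50. The 5-point harm is an assumption of this check.

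| Scenario | Rise at T2 or T3 | Risers reversed at T4 or T5 | All patients unresolved | Mean change T1 to T4 |
|---|---|---|---|---|
| No effect | 67% | 55% | 30% | 0 |
| 5-point harm, resolves fully | 84% | 61% | 32% | 0 |
| 5-point harm, persists | 84% | 38% | 52% | 5 |

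Among risers, no effect (55%) ranks below a harm that resolves (61%), because risers under no effect are more strongly selected for a low T1. With all patients as denominator the order is not inverted, but 30% remain unresolved with no harm at all. The mean change separates persistent harm from the other two cases.

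**6. All side effects together.** For the seven side-effect scores in section 15.5 (between-score correlation 0 to 0.9 assumed), no effect gives at least one rise in 82–100% of patients, and all rises reversed at T4 or T5 in 8–42% of those. For the 32 MSAS symptoms (assumed prevalence 5–30%, between-symptom correlation 0.2–0.5, serial correlation 0.5–0.8), 43–99% have a new on-treatment symptom. Of those, 39–87% have each new symptom absent at T4 or T5. The documents give no prevalences.

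**7. A threshold alone is not enough.** Counting only rises of at least 3 points, no effect still flags 54% of patients, of whom 64% are back within 3 points at T4 or T5.

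**8. Worse minus better by 3 points.** No effect: 0 at every visit, by symmetry. Where the mean shift is 5: Φ((5 − 3)/10) − Φ((−3 − 5)/10) = 0.579 − 0.212 = +0.37. A resolving harm shows +0.37 at T2 and T3 and 0 afterwards; a persistent one shows +0.37 throughout.

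**The case against.** The strongest reply is that this treats illustrative wording in an optional analysis as a decision rule. The section is headed as supportive, complete reversal is introduced as an ideal, and the all-disappeared proportion is an example of a descriptive pattern. No output listing the percentage of patients with any increment is planned. Section 15.3 also reads later decrements as amelioration, so fluctuation is not credited in one direction only. It plans no comparison of regimens on this proportion.

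Most of that stands, and it rules out three stronger readings that a reader might infer:
- *That complete reversal is the plan's criterion for recovery.* The wording does not set one.
- *That most patients would fail under a harmless regimen.* For one score under the text's own T4 or T5 rule, 55% of risers pass. Most fail at T4 alone and on the seven-score composite, but for the 32 symptoms the answer depends on prevalences that the documents do not give.
- *That the study cannot show whether harms resolve, or that this is its only patient-level look at resolution.* The same section plans visit means with confidence intervals and analyses of each of the 32 symptoms, and sections 15.7 and 15.8 model mean change to T4 and T5.

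The reply does not remove the any-increment statement, which is unqualified, or the lack of a reference value for the example summary. The symptom-level analysis starts from side effects that begin during treatment, so it makes the same selection. Ranking becomes a risk once regimen-specific figures are set side by side, which a study characterizing each regimen invites.

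A further fair criticism concerns the replacement. After treatment, relief from cure can offset persisting harm, so a net value of zero at T4 or T5 does not prove that there is no harm.

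**Conclusion.** The concern holds in limited form. The individual-level summaries in section 15.3 cannot be interpreted without a no-effect reference. Under no effect, two thirds of patients show a rise on a single score, and 30% of all patients look unresolved at T4 or T5 (42% at T4 alone). Reversal among risers can place a harmless regimen (55%) below one with a fully resolving 5-point harm (61%).

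The no-effect figures assume equal correlation across visits and continuous scores; the harm scenarios also assume normal scores, the plan's SD and correlation, and a 5-point shift chosen for illustration. A serial correlation of 0.50 covers both measurement error and real fluctuation. The primary analyses are not affected. The change is worth making because the section presents itself as an aid to interpretation and the affected figure is one that patients are likely to quote.

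**What to change.** In section 15.3:

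1. Delete the statement that any increment represents worsening or a new side effect, or qualify it by saying that individual rises also occur through ordinary fluctuation.
2. For each scale, report the proportion worse minus the proportion better than T1 by at least the plan's important difference (MSAS 0.10, PROMIS 3, HCV-PRO 10), with a confidence interval, at T2, T3, T4 and T5 separately. State the direction: a higher HCV-PRO score is better functioning. The plan gives no important difference for the headache score, so one would have to be stated.
3. For each MSAS symptom, report newly present minus newly absent relative to T1, with a confidence interval, at the same visits.
4. If the all-disappeared percentage is kept, define its terms, denominator and visit rule, show its expected value under no effect beside it with the assumptions used, and do not interpret it alone.
5. State that after treatment the net figures combine persisting harm with relief from cure.

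The cost is analysis-plan wording and a few paired tabulations from data already collected. The single all-resolved percentage would no longer be quotable on its own.
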